5.2.5 GRAFT MONITORING AND REMOVAL

Dependent upon participant response, as many as six monitoring visits will be conducted to evaluate skin thickness and adverse events (see study Schemas, page 3-4). As per the pre-IND discussion with FDA, persistence of any thickening response is of particular interest. In order to assess this, we will divide the subjects such that there will be 2 groups. The first portion will immediately have graft removal once skin thickness increases in order to assess the molecular features of induction of volar skin, and a 2nd portion of subjects will instead be followed for permanence of effect, and undergo graft removal at the conclusion of 10 months of the study.

The method of dividing the subjects will be as follows. At all monitoring visits all injected sites on all subjects will be measured for epidermal thickness by non-invasive confocal imaging or through the non-invasive measurement of skin induration (as long as those injected sites have not been removed through biopsy). The first three subjects who demonstrate a statistically significant increase of measured epidermal thickness on the volar fibroblast injected side will have their grafts removed during the follow-up visit that the increased thickness determined to be statistically significant.

The means of calculating an increase in epidermal thickness of the volar fibroblast injected site will be through a t-test statistical analysis of 3 sequential readings (within a visit) from the three injection sites (no fibroblasts, non-volar fibroblasts, and volar fibroblasts). For a subject to be designated as an “early graft removal”, he/she should have a statistically significantly elevated epidermal thickness in the volar injected site but not the non-volar or vehicle-only injected sites.

If no subjects show an increase, then all subjects will be followed for epidermal thickness till the end of the study and undergo graft removal at the end of the 10 months. If fewer than 3 subjects are identified before the end of the study to have an increase, then the remainder will undergo graft removal at the end of the study. If more than 3 subjects are identified, then those remaining subjects will be

followed through Visit 8 and undergo graft removal at the end of the 10 month period..

“Early Graft Removal” subjects will skip all remaining graft monitoring visits and instead go directly to suture removal visit.

All subjects will have at least one monitoring visit.

At each of the monitoring visits, the study team will obtain:

- Vital signs including HR, RR and BP
- Clinical photographs of the injection sites
- Measurements of injection site thickness and areas of increased thickness via Optical Coherence Tomography (OCT) or SkinFibroMeter. OCT is a non-invasive means of capturing images of superficial layers of the human skin (see Figure 8). From these images, thickness of the epidermal layer will be calculated. 3 independent measurements from each injection site in each subject will be made at every visit so that statistics can be performed (see below). SkinFibroMeter is a non-invasive, portable device utilizes an indenter that is briefly pressed on the skin. The resistance of short-term load from the skin tissue will be read by the device and the induration value of Newton will be calculated. Some visits might not include OCT imaging or SkinFibroMeter given operator and machine availability. Some exceptions can be made for unusual life events for missing a study monitoring visit.
- AE assessment/ symptom diary review

Monitoring will continue on a monthly basis for up to 5 visits in order to assess the participant’s progress and for any adverse events. At each monitoring visit, a repeat gentle skin scraping may be performed.

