5.2.5.1 GRAFT MONITORING VISIT (VISIT #7) (STUDY DAY 42 +/- 7 DAYS)

At this visit, the study team will obtain:

- Vital signs including HR, RR and BP
- Clinical photographs of the injection sites
- Thickness measurements/Area of epidermal thickness via Optical Coherence Tomography (OCT)
- Skin induration measurement via SkinFibroMeter
- AE assessment/symptom diary review
- A repeat gentle skin scraping may be performed.

5.2. 5.2GRAFT MONITORING VISIT (VISIT #8) (STUDY DAY 70 +/- 7 DAYS)

At this visit, the study team will obtain:

- Vital signs including HR, RR and BP

- Clinical photographs of the injection sites
- Thickness measurements/Area of epidermal thickness via Optical Coherence Tomography (OCT)
- Skin induration measurement via SkinFibroMeter
- AE assessment/symptom diary review
- A repeat gentle skin scraping may be performed.

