6. RISKS/BENEFITS

6.1 RISKS

6.1.1 AUTOLOGOUS VOLAR FIBROBLASTS

We expect to remove the injected cells, but cellular injections have been rarely associated with mild redness, bruising, swelling, pain, bumps, irritation and itch at the injection site in less than 10% of participants. Injection site reactions may occur including pain, bruising, swelling, erythema, pigmentation changes, induration.

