9.2.2 SECONDARY OUTCOME VARIABLES

Secondary outcome variables for this study will be 1) an increase in epidermal thickness as detected by optical coherence tomography in vivo, or by histology, and 2) an increase in KRT9 by RT-PCR, western or immunohistochemistry

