APPENDIX I- Phase One (Single Dose)

Visit/ Study Day:	Screening & Consent	Baseline	Suture removal	Graft Injection	Graft Removal / monitoring	Graft Removal / monitoring	Graft Removal ³ / monitoring	Suture Removal ²	Final evaluation				
	Day -14 Through Day -1	Visit 1 Day 0	Visit 2 Day 15 (±3 days)	Visit 3 Day 30 (±10 days)	Visit 4 Day 42 (±7 days)	Visit 5 Day 70 (±7 days)	Visit 6 Day 98 (±7 days)	Visit 7 Day 126 (±7 days)	Visit 8 Day 154 (±7 days)	Day 182 Visit 9 (±7 days)	Day 196 Visit 10 (±7 days)	Day 273 Visit 11 (±14 days)	
Informed consent	X												
Eligibility review	X	X											
Assessments													
Vital signs			X		X	X	X	X	X	X	X		
History & limited physical	X	X		X									
Medication Review	X												
Clinical Photographs		X		X	X	X	X	X	X	X	X	X	X
Biopsy/graft excision site assessment			X								X	X	
Adverse events/symptom diary review		X	X	X	X	X	X	X	X	X	X	X	X
Optical Coherence Tomography					X	X	X	X	X	X	X		
Laboratory Testing													
HIV 1 Antibody	X												
HIV 2 Antibody	X												
HIV Nucleic acid	X												
HTLV I/II Assay (Abs)	X												
Serum HCG ¹	X ¹												
Urine HCG ¹				X ¹									
Hepatitis B Surface Ag	X												
Hepatitis B, Core antibody	X												
Hepatitis C nucleic acid	X												
Procedures													
Skin biopsy		X											
Suture removal			X								X ²		
Investigational injections				X									
Excise 3 graft sites; dress graft sites ³							X ³	X ³	X ³	X			

- 1- Females of child bearing potential only
- 2- 14 days +/- 2 days after early graft removal OR study day 196 +/- 7 days
- 3- ONLY for the first three participants who exhibit statistically significant thickening based upon three OCT measurements

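### The documents contradict themselves on whether skin induration can stand in for epidermal thickness and feed the early-graft-removal test

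*Combined protocol and SAP*

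**What the plan says.** Two parts of section 5.2.5 treat induration as a way of measuring thickness. The paragraph on dividing the subjects says that sites are "measured for epidermal thickness by non-invasive confocal imaging or through the non-invasive measurement of skin induration", and its next sentence uses that measured thickness to pick the first three subjects for early removal. The list of visit procedures repeats the alternative: "Measurements of injection site thickness and areas of increased thickness via Optical Coherence Tomography (OCT) or SkinFibroMeter". It describes the second device as follows: "The resistance of short-term load from the skin tissue will be read by the device and the induration value of Newton will be calculated". It also allows for gaps: "Some visits might not include OCT imaging or SkinFibroMeter given operator and machine availability".

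Other parts keep the two measures apart or name OCT only:
- Sections 5.2.5.1 to 5.2.5.6 put OCT thickness on one line and "Skin induration measurement via SkinFibroMeter" on another.
- Section 9.2.2 defines the secondary outcome as "an increase in epidermal thickness as detected by optical coherence tomography in vivo, or by histology".
- Footnote 3 of the Phase One schedule (Appendix I) limits early excision to thickening "based upon three OCT measurements". The Phase Two schedule (Appendix II) carries the same footnote. Both tables have an OCT row and no SkinFibroMeter row.

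Section 9.2 (the t-tests) and section 4.4.2 (treatment failure) name no device.

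On safety, section 6.1.1 says: "Injection site reactions may occur including pain, bruising, swelling, erythema, pigmentation changes, induration".

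**The concern.** A force reading and a layer thickness are different quantities. Firmness of the skin can rise because of swelling or a dermal reaction with no change in the epidermis, and the protocol itself expects induration after injection. If an induration reading is accepted as thickness, the same finding could be recorded as an adverse event and also taken as the sign that the volar cells are working.

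The decision that hangs on this cannot be undone. A subject who meets the rule has all three sites excised and skips the remaining monitoring visits. Persistence of thickening is secondary objective 3, and 5.2.5 singles it out as a matter raised in the pre-IND discussion with FDA. There are only three early-removal places, and they exist to supply responding skin for the molecular work. A place filled on induration alone may supply skin that has not thickened and removes that subject from the persistence data.

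**Working it through.** **1. The sections side by side**

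| Place | Thickness measured by | Measure behind early removal |
|---|---|---|
| 5.2.5, dividing the subjects | Imaging or induration | Whatever was measured as thickness |
| 5.2.5, visit procedures | OCT or SkinFibroMeter | Not stated there |
| 5.2.5.1 to 5.2.5.6 | OCT; induration listed separately | Not stated |
| 9.2 | No device named | No device named |
| 9.2.2 | OCT or histology | Not applicable |
| Appendices I and II, footnote 3 | OCT | Three OCT measurements |

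Two people following 5.2.5 and the footnotes respectively could reach opposite decisions from the same induration-only visit. Section 9.2 does not settle it.

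**2. The plan's own figure**

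The documents give no figure for this point. The nearest is the power statement in 9.2: difference 2, SD 0.5, alpha 0.06, power 0.8, n = 3. For a two-sided unpaired t-test the noncentrality is 2 / (0.5 × √(2/n)), which is 4.00 for n = 2 (2 df) and 4.90 for n = 3 (4 df). Power is 0.63 and 0.96, so 3 is the smallest n that reaches 0.8 and the figure reproduces. Its difference and SD carry no unit or device, so they cannot be used to size an induration effect.

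**3. How the rule responds to a reaction (illustration)**

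Inputs from 5.2.5 and 9.2: three readings per site per visit, t-tests at 0.05, and a rise required at the volar site but not at the other two. Sidedness is not stated; two-sided tests were assumed. For two sites, t = (m₁ − m₂) / √((s₁² + s₂²)/3) on 3 + 3 − 2 = 4 df, with critical value 2.776. Readings were assumed normal with equal SD within each site, and 400,000 visits were simulated per scenario. Rises are in within-site SDs and are assumptions.

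The text does not say what a site must be compared with to count as raised, so two readings were tried. Strict: volar above non-volar, volar above vehicle, and non-volar not above vehicle. Loose: volar above vehicle, and non-volar not above vehicle.

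| Rise (SDs) | Strict, volar site only | Strict, both cell sites equally | Loose, volar site only | Loose, both cell sites equally |
|---|---|---|---|---|
| 0 | 0.4% | 0.4% | 2.1% | 2.1% |
| 1 | 5.8% | 1.2% | 14% | 9.7% |
| 2 | 28.8% | 1.3% | 44% | 16.8% |
| 3 | 64.9% | 0.7% | 76% | 11.6% |
| 4 | 88.7% | 0.2% | 92% | 3.8% |

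A rise shared by all three sites leaves the rate at about 0.4% (strict) or 2% (loose). A reaction present at both cell sites but larger at the volar one was not simulated. These rates take the sites as equal before any reaction. With no effect but between-site SDs of 1, 2 or 3 reading SDs, the strict rule is met at 3.7%, 9.4% and 12.6% of visits, and that would apply to either device.

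**4. The cap on early removals**

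The documents do not say whether the first three subjects are counted per phase or over the trial: 3/20 = 15%, 3/80 = 3.75%, or 3/100 = 3%.

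**The case against.** Several stronger readings are tempting, and the documents do not support them.

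- A reader might infer that an injection-site reaction is scored as efficacy. Section 9.2.2 says otherwise: the outcome is OCT or histology. The only opening is that 9.2 and 4.4.2 use the term epidermal thickness without naming a device while 5.2.5 lets induration carry that label.
- A reader might infer that Newton values and thickness values are pooled in the final t-test. Nothing in the text says so.
- A reader might infer that any injection-site reaction can trigger removal. All three sites are injected and two receive cells, and 6.1.1 does not tie induration to volar cells. The condition on the other two sites blocks most shared reactions under either reading above, though less firmly under the loose one.
- A reader might take 15% of Phase One subjects as the size of the problem. That is one version of the cap on early removals whichever device is used; no share of it is shown to come from induration.

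It can also be argued that the footnotes govern the excision, and that the sentence in 5.2.5 on three readings follows the description of OCT and so may mean OCT readings. That is a reasonable reading, but 5.2.5 also says in terms that induration is an alternative, and no order of precedence is given.

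On timing, if the schedule columns are read in order, early excision is marked only from Day 98. That is 98 − 30 = 68 days after the Phase One injection and 98 − 59 = 39 days after the last Phase Two injection. The documents do not show that induration lasts so long. This lowers the likely exposure, although the text of 5.2.5 sets no earliest day and places removal at the visit where the increase is found.

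Finally, the staff who measure are blinded to site identity (4.1.1). That protects against biased reading but does not change what the device measures.

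**Conclusion.** The contradiction is certain: 5.2.5 allows a force reading to be called epidermal thickness and passes it to an irreversible decision, while 9.2.2 and both schedule footnotes do not. The consequence is conditional. It needs a visit without OCT, staff acting on 5.2.5 rather than on the footnote, and a reaction larger at the volar site than at the other two. Where all three hold, a subject can be lost from persistence follow-up and an early-removal place used without evidence of thickening.

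The frequency cannot be derived, because the documents give neither the variability of SkinFibroMeter readings nor the share of visits without OCT. The simulated rates show only how the rule behaves under assumed rises. The primary outcome, tolerability, is not redefined by this, and all grafts are due for excision in any case. What is exposed is the persistence objective and the choice of tissue for the early molecular analysis.

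**What to change.** 1. In both places in 5.2.5, stop describing induration or the SkinFibroMeter as a measure of epidermal thickness.
2. In 9.2, state that the thickness analysis uses OCT or histology, in line with 9.2.2, and have 4.4.2 refer to the same definition.
3. Report SkinFibroMeter values separately, in their own unit and under their own name, as a descriptive measure.
4. Reconcile 5.2.5, 9.2 and footnote 3 of both schedules on which measurement feeds the early-removal test. The sponsor must settle that rule; this review does not propose one. The agreed text should also say what a visit means for the rule when that measurement is missing.

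The cost is wording only, with fewer usable thickness readings at visits where OCT is unavailable.

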5.2.5.1 GRAFT MONITORING VISIT (VISIT #7) (STUDY DAY 42 +/- 7 DAYS)

At this visit, the study team will obtain:

- Vital signs including HR, RR and BP
- Clinical photographs of the injection sites
- Thickness measurements/Area of epidermal thickness via Optical Coherence Tomography (OCT)
- Skin induration measurement via SkinFibroMeter
- AE assessment/symptom diary review
- A repeat gentle skin scraping may be performed.

5.2. 5.2GRAFT MONITORING VISIT (VISIT #8) (STUDY DAY 70 +/- 7 DAYS)

At this visit, the study team will obtain:

- Vital signs including HR, RR and BP

- Clinical photographs of the injection sites
- Thickness measurements/Area of epidermal thickness via Optical Coherence Tomography (OCT)
- Skin induration measurement via SkinFibroMeter
- AE assessment/symptom diary review
- A repeat gentle skin scraping may be performed.

5.2.5.3 GRAFT MONITORING VISIT (VISIT #9) (STUDY DAY 98 +/- 7 DAYS)

At this visit, the study team will obtain:

- Vital signs including HR, RR and BP
- Clinical photographs of the injection sites
- Thickness measurements/Area of epidermal thickness via Optical Coherence Tomography (OCT)
- Skin induration measurement via SkinFibroMeter
- AE assessment/symptom diary review
- A repeat gentle skin scraping may be performed.

5.2.5.4 GRAFT MONITORING VISIT (VISIT #10) (STUDY DAY 126 +/-7 DAYS)

At this visit, the study team will obtain:

- Vital signs including HR, RR and BP
- Clinical photographs of the injection sites
- Thickness measurements/Area of epidermal thickness via Optical Coherence Tomography (OCT)
- Skin induration measurement via SkinFibroMeter
- AE assessment/symptom diary review
- A repeat gentle skin scraping may be performed.

5.2.5.5 GRAFT MONITORING VISIT (VISIT #11) (STUDY DAY 154 +/- 7 DAYS)

At this visit, the study team will obtain:

- Vital signs including HR, RR and BP
- Clinical photographs of the injection sites
- Thickness measurements/Area of epidermal thickness via Optical Coherence Tomography (OCT)
- Skin induration measurement via SkinFibroMeter
- AE assessment/symptom diary review
- A repeat gentle skin scraping may be performed.

5.2.5.6 GRAFT REMOVAL VISIT (VISIT #12) (STUDY DAY 182 +/-7 DAYS)

At this visit, the study team will obtain:

- Vital signs including HR, RR and BP
- Clinical photographs of the injection sites
- Thickness measurements/Area of epidermal thickness via Optical Coherence Tomography (OCT)
- Skin induration measurement via SkinFibroMeter
- AE assessment/symptom diary review
- Graft removal will be performed as was the initial biopsy and is detailed in Appendix VII.

5.2.6 SUTURE REMOVAL VISIT (VISIT #13) (STUDY DAY 196 +/- 7 DAYS OR 14 DAYS +/-2 AFTER EARLY GRAFT REMOVAL)

All participants with the exception of those who undergo early graft removal will return for suture removal at this time point. “Early graft removal” participants will return to have sutures removed 14 days (+/- 2 days) after their graft removal. “Early graft removal” subjects will have fewer graft monitoring visits, but will be expected to return for a final evaluation visit (see Visit 11).

5.2.7 FINAL EVALUATION VISIT (VISIT #14) (STUDY DAY 273 +/- 14 DAYS)

At day 273 (+/- 14 days) after the subject’s initial injection the participant will return for the following:

- Graft excision site evaluation/wound healing.
- AE assessment

Subjects who have an “Early graft removal” will be expected to return at this time for monitoring also.

6. RISKS/BENEFITS

6.1 RISKS

6.1.1 AUTOLOGOUS VOLAR FIBROBLASTS

We expect to remove the injected cells, but cellular injections have been rarely associated with mild redness, bruising, swelling, pain, bumps, irritation and itch at the injection site in less than 10% of participants. Injection site reactions may occur including pain, bruising, swelling, erythema, pigmentation changes, induration.

6.1.2 DMSO INJECTION

We have been injecting 5% DMSO in vehicle with no adverse events. When used at very high doses (such as large volumes of 100%), the risks of DMSO include

bad breath, and changes in the skin (like redness, itching, hives, dryness, and rarely blisters). Very rarely people may feel sedated, have headaches or nausea. However, we have not observed any of these effects. Adverse events will be notified to the FDA and IRB.

6.1.3 PUNCH BIOPSY

Common risks of skin biopsies include potential bleeding, pain or discomfort, and a slight risk of infection at the biopsy site. As with any cut in the skin, a scar will develop, although its appearance will likely fade over time.

We will screen carefully for keloids in our exclusion criteria, but in rare individuals with no prior keloid history, keloids or excessive scarring may develop at the biopsy site.

6.1.4 BLOOD DRAW

Taking blood may commonly cause discomfort, bleeding, or bruising where the needle enters the body.

In rare cases, it may result in fainting. There is also a small risk of infection at the draw site.

6.1.5 LIDOCAINE WITH EPINEPHRINE

Although very rare (less than 1% of individuals), it is possible that a participant may have an allergic reaction to the local anesthetic (lidocaine) used to numb the skin prior to a punch biopsy. A reaction of this kind would cause swelling and a rash on the participant skin where the anesthetic was injected.

6.1.6 FINANCIAL RISK

There is a slight financial risk to the participants in the rare event that the above complications occurs requiring additional medical care.

6.1.7 CONFIDENTIALITY

There is a potential risk to confidentiality. Most participant related data will be stored in our institution's electronic medical record. If members from the IRB or other Federal agencies need to inspect trial records, they will be released. Hence, absolute confidentiality cannot be guaranteed.

6.1.8 TATTOOS

The tattoo markings will be permanent and will have the appearance of a dark freckle until we excise the injection sites during the graft removal visit (see section 5.2.5.6). While the markings are being created, the needle may cause discomfort, like a small pinch or insect bite.

6.2 STEPS TAKEN TO MINIMIZE RISK

6.2.1 AUTOLOGOUS VOLAR FIBROBLASTS

Injected cells will meet all required release criteria for clinical use before injection (see IND application which includes steps of verifying purity, sterility and potency) by the Hopkins Cellular Therapy Core. Additionally, we will remove the injected site via biopsy in order to avoid any theoretical long-term problems from injected cells. Finally, all participants will be closely monitored for adverse events throughout the study.

6.2.2 DMSO INJECTION

We find that DMSO enhances engraftment of cells, and have already been injecting it in our vehicle so we consider it safe. However, to minimize risk, we will only use an FDA approved (for interstitial cystitis and intravesical delivery) of DMSO formulation (RIMSO-50). We will only inject small volumes (maximum 1 ml). We will monitor the participants to ensure safety and to avoid any potential side effects induced by the DMSO.

6.2.3 PUNCH BIOPSY

Only [name], a trained dermatologist, will perform the biopsy procedures. We will screen carefully for keloids in our exclusion criteria, but in rare individuals with no prior keloid history, keloids or excessive scarring may develop at the biopsy site.

6.2.4 BLOOD DRAW

Blood draws for this study will be done by trained phlebotomists in order to reduce the potential risks associated with the procedure.

